3.3. Other Endpoint(s)

3.3.1. Additional Plasma PF-07293893 Parameters

Additional plasma PF-07296893 PK parameters, as described in Table 3, will be determined.

Table 3. Additional PF-07293893 PK Parameters

Parameter	Definition	Method of Determination	Analysis Scale	PF-07293893
CL/F^*	Apparent clearance	Dose/AUC_{inf}	ln	D
V_z/F^*	Apparent volume of distribution	Dose/($AUC_{inf} \times kel$)	ln	D
$AUC_{last}(dn)$	Dose-normalized AUC_{last}	$AUC_{last}/Dose$	ln	D
$AUC_{inf}(dn)^*$	Dose-normalized AUC_{inf}	$AUC_{inf}/Dose$	ln	D
$C_{max}(dn)$	Dose-normalized C_{max}	$C_{max}/Dose$	ln	D

Key: ln=natural-log transformed,
 D=displayed with descriptive statistics,
 *=if data permit

3.3.2. Plasma PF-07293893 PK parameters during crystalline form period if conducted

The plasma PF-07296893 PK parameters described in [Table 2](#) and dose normalized PK parameters (if required) in [Table 3](#) will also be determined after crystalline PF-07293893 oral suspension administration.

3.3.3. Transporter biomarkers (optional)

Transporter biomarkers (eg, [CCI](#)) will be analyzed if feasible and deemed necessary. The AUC_{24} and C_{max} of each transporter biomarker will be derived if applicable, where the analysis scale is ln.

3.4. Baseline Variables

Not applicable.

3.5. Safety Endpoints

See Section [3.1](#) for details.

4. ANALYSIS SETS (POPULATIONS FOR ANALYSIS)

Data for all participants will be assessed to determine if participants meet the criteria for inclusion in each analysis population prior to unblinding and releasing the database and classifications will be documented per standard operating procedures.

Participant Analysis Set	Description	Applicable Analysis (for additional information refer to section 6)
Enrolled	"Enrolled" means a participant's, agreement to participate in a clinical study following completion of the informed consent process and randomization to study intervention. A participant will be considered enrolled if the informed consent is not withdrawn prior to participating in any study activity after screening. Potential participants who are screened for the purpose of determining eligibility for the study, but do not participate in the study, are not considered enrolled, unless otherwise specified by the protocol.	
Safety analysis set	All participants randomly assigned to study intervention and who take at least 1 dose of study intervention. Participants will be analyzed according to the study intervention they actually received.	Section 6.1 Safety endpoints summaries and analyses

Participant Analysis Set	Description	Applicable Analysis (for additional information refer to section 6)
PK Concentration Set	All participants randomly assigned to study intervention and who receive at least 1 dose of study intervention and in whom at least 1 plasma concentration value is reported.	Section 6.2, Section 6.3.1, Section 6.3.2 PK endpoints
PK Parameter Set	All participants randomly assigned to study intervention and who receive at least 1 dose of study intervention and have at least 1 of the PK parameters of interest calculated.	Section 6.2, Section 6.3.1, Section 6.3.2 PK endpoints
Biomarker Concentration Set	All participants randomly assigned to study intervention and who receive at least 1 dose of study intervention and in whom at least 1 plasma biomarker concentration value is reported.	Section 6.3.3 Biomarker endpoints
Biomarker Parameter Set	All participants randomly assigned to study intervention and who receive at least 1 dose of study intervention and have at least 1 of the Biomarker parameters of interest calculated.	Section 6.3.3 Biomarker endpoints

5. GENERAL METHODOLOGY AND CONVENTIONS

5.1. Hypotheses and Decision Rules

There is no statistical hypothesis testing planned for this study, and no statistical decision rules will be applied.

5.2. General Methods

Unless otherwise stated, all summaries and plots will be presented by dose and treatment. Each formulation of PF-07293893 administered during the study and fasting status will be considered as separate treatments. If a dose level is repeated across 2 or more cohorts, the data will be combined, unless the dose is in a different formulation or food state, in which case the dose would be reported separately.

Unless otherwise stated, the summary tables and/or statistical analyses will only include a single pooled placebo group across all included cohorts with SDD formulation. Placebo will be pooled from all dose escalation periods but not for the fed period (if conducted) nor for crystalline formulation period (if conducted).

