Screening activities will be completed over the 28 days prior to randomization in Period 1. Participants confirming eligibility according to [Section 5](#) will be admitted to the CRU on Day -1 in Period 1 for each cohort. For each period in this study, on Day 1, following ≥ 10 hour overnight fast, participants will receive a single oral dose of PF-07293893 or placebo. Participants will be discharged on Day 4, following completion of all scheduled assessments (approximately 72 hours post-dose). Participants may be asked to remain in the CRU after completion of Day 4 activities at the discretion of the investigator or if safety, tolerability, or PK data dictate the need to prolong confinement in the CRU. In each cohort, a washout interval of at least 7 days will be introduced between subsequent doses. During the washout interval, emerging 24-hour PK and 72-hour safety data will be reviewed and the next dose will be determined. An on-site follow-up visit will occur on Day 8 ± 1 after the final dose. The follow-up contact may occur via telephone contact and must occur 28–35 days after administration of the final dose of study intervention. The total planned duration of participation from the screening visit to the telephone follow-up contact will be approximately 14 weeks.

Based on the review of emerging safety, tolerability, and PK data in Cohorts 1 and 2, the remaining periods of Cohort 2 and/or an optional third cohort enrolling approximately 8 participants (crossover, placebo controlled design) may be used to explore additional doses, to repeat a dose, or to evaluate effect of crystalline form on PF-07293893 PK in fasted and/or fed state.

Dosing will occur in the fasted state for all periods, except if an optional exploratory assessment of the effect of food on crystalline PF-07293893 PK is conducted. The actual dose level for the assessment of food effect will be selected based on emerging safety, tolerability, and PK data but will be expected to achieve projected therapeutic exposures ([Section 4.3.2](#)).

If a participant drops out before completing all study periods within a cohort, or withdraws for a reason unrelated to safety, the participant may be replaced at the discretion of the investigator and sponsor. The replacement participant(s) may or may not be required to complete all periods of the cohort in which they are participating at the discretion of the investigator and sponsor.

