6.1.1. Adverse Events

Adverse events will be listed and summarized by dose and treatment (if applicable) and overall, in accordance with sponsor reporting standards using the safety analysis set defined in Section 4.

The AEs will be presented sorted in descending frequency based on the overall number of AEs (by preferred term or system order class as appropriate) across treatments.

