6.1.4. Continuous Cardiac Monitoring

Data will be reviewed and summarized on an ongoing basis during the study to evaluate the safety of participants.

All abnormal rhythms will be recorded and reviewed by the investigator for the presence of rhythms of potential clinical concern. The time, duration, and description of the clinically significant event will be recorded in the CRF. Events deemed of clinical concern will be recorded as AEs and will be summarized as part of the standard AE outputs.

6.1.5. 12-Lead ECG

Absolute values and CFB in QT, heart rate, QTcF, PR and QRS will be summarized by dose and treatment and timepoint using sponsor reporting standards, using the safety analysis set defined in Section 4. Baseline is as defined in Section 3.1.5.

Mean CFB in QT, heart rate and QTcF will be plotted against time post-dose. On each plot there will be one line for each treatment. Corresponding individual plots of CFB will also be produced for each treatment.

Changes from baseline in QTcF will also be plotted separately against drug concentrations of PF-07293893. This will be a scatter plot for all observations where QTcF and drug concentration are recorded. Placebo data will also be included (with drug concentration set to zero). Different symbols will be used for each treatment.

Maximum increase from baseline for QTcF, heart rate, PR and QRS values will be summarized by dose and treatment, according to sponsor reporting standards.

ECG endpoints and CFB (QTcF, PR and QRS) will also be summarized descriptively by dose and treatment using categories as defined in Appendix 1. Numbers and percentages of participants meeting the categorical criteria will be provided. All planned and unplanned postdose time points will be counted in these categorical summaries.

Values meeting the categorical criteria occurring pre-dose on Day 1 for each period starting with Period 2, will be attributed to the treatment from the previous period (e.g., for cohort 1, an occurrence pre-dose at Period 2 Day 1 will be attributed to the Period 1 dose).

Listings of participants with any single post-dose value >500 msec will also be produced for QTcF.

Data collected at screening that are used for inclusion/exclusion criteria, will be considered source data, and will not be required to be reported, unless otherwise noted.

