- median concentration-time plots (on both linear and semi-log scales) against nominal time post-dose by dose (all doses on the same plot per scale, based on the summary of concentrations by dose and time post-dose) and treatment (if applicable).
- mean concentration-time plots (on both linear and semi-log scales) against nominal time post-dose by dose (all doses on the same plot per scale, based on the summary of concentrations by dose and time post-dose) and treatment (if applicable).

The scale used for the x-axis (time) of these plots will be decided on review of the data, and will depend on how long PF-07293893 concentration is quantifiable in the matrix.

For summary statistics, median and mean plots by sampling time, the nominal PK sampling time will be used. For individual participant plots by time, the actual PK sampling time will be used.

To assess any food effect in SDD formulation as a tertiary objective, a mixed effects model will be performed separately on the natural log transformed AUC_{inf} , AUC_{last} , and C_{max} with fasting condition included as a fixed effect and participant as a random effect as described in Section 5.2.3. Only data from the respective periods in the cohort 3 will be included. The fasted state will be the reference and the fed state will be the test treatment.

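### Does SAP 5.2 leave placebo data from fed, crystalline and repeat-dose periods without a defined place in the tables?

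*SAP*

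**What the plan says.** SAP 5.2 (General Methods) presents summaries and plots by dose and treatment, and counts each formulation and each fasting status as its own treatment. A dose level given in two or more cohorts is combined, unless formulation or food state differs, in which case it is reported separately.

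Two sentences on placebo follow. The first, subject to any statement elsewhere to the contrary, says that "the summary tables and/or statistical analyses will only include a single pooled placebo group across all included cohorts with SDD formulation". The second says: "Placebo will be pooled from all dose escalation periods but not for the fed period (if conducted) nor for crystalline formulation period (if conducted").

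Other sections bear on the point:

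- SAP 6.1.1: "Adverse events will be listed and summarized by dose and treatment (if applicable) and overall", on the safety set. For that set, SAP 4 says: "Participants will be analyzed according to the study intervention they actually received".
- SAP 6.2, on the SDD food-effect model: "Only data from the respective periods in the cohort 3 will be included". Fasted is the reference and fed is the test.
- SAP 6.1.5, on the plot of QTcF change against concentration: "Placebo data will also be included (with drug concentration set to zero"), and "Different symbols will be used for each treatment".
- Protocol 4.1: the remaining Cohort 2 periods and/or Cohort 3 "may be used to explore additional doses, to repeat a dose, or to evaluate effect of crystalline form" in the fasted or fed state.

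**The concern.** Safety is the primary endpoint, and placebo is the only comparator in its tables. Three things look unsettled.

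1. Fed-period and crystalline-period placebo is kept out of the pool, and no section then says whether it has its own column or is only listed. If the first placebo sentence is taken at full strength, with one placebo group and no other, those recipients count in the overall column of the adverse event table but in no treatment column.
2. The first sentence defines the pool by SDD cohorts and the second by dose escalation periods. A fasted SDD period that repeats or lowers a dose, or that serves as the Cohort 3 fasted reference, fits the first. The second neither includes nor excludes it by name.
3. The QTcF plot gives each treatment its own symbol but does not say whether fed and crystalline placebo are treatments of their own.

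At stake is whether two programmers working from the same SAP would build the same placebo denominator.

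**Working it through.** **Reproducing the plan's figure.** A cohort has about 8 participants, randomized 3:1 in each period (Protocol 4.1). Active: 8 × 3/4 = 6. Placebo: 8 × 1/4 = 2. This matches the 6 and 2 in Protocol 4.2 and 9.5.

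**Placebo doses in total.** There are four periods per cohort and 2 placebo doses per period.

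- Two cohorts: 2 × 4 × 2 = 16.
- Three cohorts: 3 × 4 × 2 = 24.

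These are administrations. A participant may receive placebo up to twice, so participant denominators can be smaller.

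**Where each kind of period falls under the two sentences.**

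| Period | First sentence (SDD cohorts) | Second sentence (escalation periods) |
|---|---|---|
| Fasted SDD, escalating | in the pool | in the pool |
| Fasted SDD, repeated or lower dose | in the pool | not named |
| Fed SDD | SDD cohort | excluded |
| Crystalline, fasted or fed | outside SDD | excluded |

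Row 1 is settled. In row 2 the sentences do not conflict, because the second removes only fed and crystalline periods. Footnote b to the SAP study schema says that SDD is the formulation used for escalation and contrasts it with crystalline periods, so the escalation periods can be read as the fasted SDD part of the study. In rows 3 and 4 the data are out of the pool, and the separate-treatment rule in the same section points to separate display.

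**Smallest SDD food-effect layout.** Take one fed and one non-escalating fasted SDD period in Cohort 3.

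- Fed placebo with no stated column: 1 × 2 = 2 doses.
- Fasted placebo in doubt for the pool: 1 × 2 = 2 doses.
- Assumption A, one escalation period for each of the six doses in Protocol Table 3: the pool is 6 × 2 = 12, or 12 + 2 = 14. The difference is 2/12 = 16.7%.
- Assumption B, all eight Cohort 1 and 2 periods escalate: the pool is 8 × 2 = 16, or 16 + 2 = 18. The difference is 2/16 = 12.5%.
- If every period escalates, the difference is 0.

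In display terms, one event in the pool would read 1/12 = 8.3% or 1/14 = 7.1% per placebo dose.

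Larger counts come from treating every period not needed for escalation as affected. They are not a measure of the problem, since Protocol 4.1 also lets those periods explore additional doses, and the schema figure that would show the layout is not available.

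**What uses the pool.**

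- SAP 5.1: no hypothesis test and no statistical decision rule.
- Protocol 6.6.1: the stopping criteria rest on events in participants on active drug, on exposures and on clinical judgement. None uses a pooled placebo rate.
- SAP 6.2 and 6.3.2: the food-effect models compare PK of the active drug, fed against fasted.

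The pool therefore feeds descriptive safety displays and, if analyzed, the transporter biomarker summaries.

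**The QTcF plot.** The single-pool sentence governs summary tables and statistical analyses. Plots fall under the opening rule of SAP 5.2, by dose and treatment with fasting status separate, and SAP 6.1.5 adds a symbol per treatment. No gap remains there.

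**The case for a change.** The best argument for a change is that the SAP does not actually state the convention. The separate-treatment rule is worded for formulations of PF-07293893 and for fasting status, and does not mention placebo. The combining rule speaks of a dose level repeated across cohorts, and again placebo is not named. The sentinel-dosing text does distinguish escalating periods from those that repeat or lower a dose, so a strict reader may do the same in SAP 5.2. That reader would combine active data from a repeated dose while leaving the placebo given in the same period out of the pool. The case is also a live one: SAP version 2 was issued to add the SDD food effect, and Cohort 3 keeps a placebo-controlled design. One or two sentences would close the gap at almost no cost.

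The wording gap stands. Its consequence does not. Nothing in SAP 5.2 drops the unpooled placebo: the safety set keeps everyone dosed, and adverse events, laboratory data and vital signs are all listed. Protocol 6.1 lists placebo as an intervention at 0 mg, prepared alongside both the SDD and the crystalline suspensions, so carrying the formulation and food-state rule over to placebo is the obvious step. That the choice falls to one programmer is also not established, because SAP 6.1 sends these displays to the sponsor's reporting standards. With about 2 placebo participants per period, no version of the table could separate a food effect from a drug effect.

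**Conclusion.** The concern is correct as an observation about wording and does not call for a change. SAP 5.2 names no column for fed-period and crystalline-period placebo, and its phrase for the pool does not expressly cover fasted SDD periods that repeat or lower a dose. Both gaps have one sensible filling, which the rest of the section supports: pool placebo from all fasted SDD periods, and show the other placebo beside the matching active treatment. Writing that down would record what an analyst would do anyway and would alter no inference.

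The size is about 2 placebo doses without a stated column and about 2 in doubt in the smallest SDD food-effect layout. This rests on 2 placebo per period, on one fed and one non-escalating fasted SDD period in Cohort 3, and on six or eight escalation periods. More such periods would raise the counts, and escalation throughout would bring them to zero. The actual layout cannot be checked, because the schema figure and the December 2023 administrative change letter are not available.

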3. ENDPOINTS AND BASELINE VARIABLES: DEFINITIONS AND CONVENTIONS

3.1. Primary Endpoint(s)

Primary endpoints include assessment of adverse events (AEs), clinical safety laboratory tests, vital signs, continuous cardiac monitoring, 12-lead electrocardiograms (ECG), physical examinations and neurological examinations during the entire study, by period.

Any events occurring following start of study intervention (ie, treatment with PF-07293893 or placebo) will be counted as treatment emergent.

Events that occur in a non-treatment period (eg, washout or follow-up) will be counted as treatment emergent and attributed to the most recent treatment taken.

A 3-tier approach for summarizing adverse events will not be used due to the low number of participants planned to be recruited.

The following data are considered in standard safety summaries (see protocol for collection days and list of parameters):

- adverse events,
- laboratory data (except data from screening visit),
- vital signs data,
- ECG results,
- cardiac monitoring,
- physical examinations,
- neurological examinations.

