3.1.3. Vital Signs

Single supine blood pressure will be measured at screening, follow-up visit and early termination (ET; if applicable). Triplicate supine measurements will be taken at all other times as specified in the Schedule of Activities (SoA) of the protocol. The average of the triplicate measurements will be calculated prior to analyzing the data. Respiratory rate, pulse rate and temperature will be measured at each timepoint specified in the protocol.

Baseline for these measures will be defined as the last pre-dose measurement in each study period.

The following endpoints will be determined:

- Change from baseline in systolic and diastolic BP, pulse rate, temperature, and respiratory rate
- The minimum and maximum post-dose systolic and diastolic BP, pulse rate, temperature, and respiratory rate
- The maximum increase and decrease from baseline over all measurements taken postdose for systolic and diastolic BP, pulse rate, temperature, and respiratory rate values

The maximum increase from baseline will be calculated by selecting the maximum CFB over the respective period, except in the case where a participant does not show an increase. In such an instance, the minimum decrease should be taken. Similarly, the maximum decrease from baseline will be determined by selecting the minimum value of the CFB. In cases where a participant does not show a decrease, the minimum increase should be taken.

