3.1.4. Continuous Cardiac Monitoring

Continuous cardiac monitoring will be performed using telemetry as outlined in the protocol.

All abnormal rhythms will be recorded and reviewed by the study physician for the presence of rhythms of potential clinical concern. The time, duration, and description of the clinically significant event will be recorded in the CRF.

Events deemed of clinical concern will be recorded as AEs and will be summarized as part of the standard AE outputs.

3.1.5. 12-Lead ECG

A single 12-lead ECG will be obtained on all participants at screening, follow-up visit and at ET (if applicable). 12-lead ECGs will be recorded in triplicate at all other times as specified in the the protocol. The average of the triplicate readings collected at each assessment time will be calculated for each ECG parameter. If one or two of the triplicates are missing, the non-missing values will be used for the average, and missing values will not be imputed.

The mean of the three averages of *the triplicate ECG measurements collected at -1.0, -0.5, and 0 hours pre-dose on Day 1 of each period will serve as each participant's baseline value for that period.* If one or two of the averages are missing, the non-missing averages will be used for the mean, and missing values will not be imputed.

ECG endpoints include heart rate, QT interval, PR interval and QTcF and QRS complex. If not supplied QTcF will be derived using Fridericia's heart rate correction formula:

QTcF (msec) = QT (msec) / (RR)^{1/3}, where RR (sec) = 60/Heart Rate (if RR not provided).

The following endpoints will be determined:

- Change from baseline in QT, QTcF, PR, QRS interval and heart rate
- The maximum post-dose QTcF, heart rate, PR and QRS interval
- The maximum increase from baseline over all measurements taken post-dose for QTcF, heart rate, PR and QRS values

The maximum increase from baseline will be calculated by selecting the maximum change from baseline over the respective period, except in the case where a participant does not show an increase. In such an instance, the minimum decrease should be taken.

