5.2.2. Analyses for Categorical Endpoints

Categorical variables will be presented using summary statistics: number of observations and percentages.

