6.1.3. Vital Signs

Absolute values and CFB in supine systolic and diastolic BP, pulse rate, temperature and respiratory rate will be listed and summarized by dose and treatment and timepoint, according to sponsor reporting standards, using the safety analysis set defined in Section 4. Baseline is as defined in Section 3.1.3.

Mean absolute values and CFB for supine systolic and diastolic BP, pulse rate, temperature, and respiratory rate will be plotted against time point. On each plot there will be one line for each treatment with all treatments on the same plot. Corresponding individual plots of changes from baseline will also be produced for each treatment.

Maximum increase and decrease from baseline over all measurements taken post-dose for supine systolic and diastolic BPs, pulse rate, temperature and respiratory rate will be summarized by treatment, according to sponsor reporting standards.

Minimum and/or maximum absolute values and CFB for supine vital signs will also be summarized descriptively by treatment using categories as defined in Appendix 1. Numbers and percentages of participants meeting the categorical criteria will be provided. All planned and unplanned post-dose time points will be counted in these categorical summaries. All values meeting the criteria of potential clinical concern will be listed.

Values meeting the categorical criteria occurring pre-dose on Day 1 for each period starting with Period 2, will be attributed to the treatment from the previous period (e.g., for Cohort 1, an occurrence pre-dose at Period 2 Day 1 will be attributed to the Period 1 dose).

Data collected at screening that are used for inclusion/exclusion criteria, will be considered source data, and will not be required to be reported, unless otherwise noted.

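### Does counting participants rather than periods in the vital-sign and ECG category tables distort the pooled placebo column enough to need a change?

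*SAP*

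**What the plan says.** **Pooling.** SAP 5.2 states that, by default, "the summary tables and/or statistical analyses will only include a single pooled placebo group across all included cohorts with SDD formulation", and limits the group by source: "Placebo will be pooled from all dose escalation periods but not for the fed period", nor for a crystalline period.

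**Unit in the tables themselves.** SAP 6.1.3 (vital signs) states: "Numbers and percentages of participants meeting the categorical criteria will be provided". SAP 6.1.5 repeats this for QTcF, PR and QRS. Protocol 9.3.1.1 also tabulates QTcF categories as participants by treatment. Planned and unplanned post-dose time points all count.

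**Unit elsewhere.** SAP 5.2.2 gives a general convention: "Categorical variables will be presented using summary statistics: number of observations and percentages". SAP 3.1 sets the safety endpoints "neurological examinations during the entire study, by period". SAP 3.1.3 says "The maximum increase from baseline will be calculated by selecting the maximum CFB over the respective period", and SAP 3.1.5 says "The maximum increase from baseline will be calculated by selecting the maximum change from baseline over the respective period".

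**Outside standards.** Neighbouring paragraphs of SAP 6.1.3 and 6.1.5 defer to sponsor conventions; the extreme changes in vital signs, for instance, "will be summarized by treatment, according to sponsor reporting standards". Those standards are not among the documents.

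**Layout.** Protocol 4.1 and 9.5 plan 6 active and 2 placebo participants per dose level, with at most four active and two placebo doses per person.

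**The concern.** Two things look wrong. First, the general rule speaks of observations and the endpoint definitions work by period, whereas the table sections speak of participants. Someone with two placebo periods has two baselines and two maxima that fall into one pooled column, and no supplied text says whether that is one record or two.

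Second, if such a person counts once, the comparison is uneven. The pooled placebo column gives that person two chances to meet a criterion, while a planned dose column gives each person one (unless a dose is repeated in the same person). The expected placebo percentage rises, and a drug effect on blood pressure, pulse or QTcF looks smaller beside it. These tables belong to the primary safety summary, and protocol 2.2.5 reports blood pressure and heart rate effects in dogs, so the placebo comparator matters to a reader.

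**Working it through.** **Layout.** 3 cohorts × 8 = 24 participants, and 8 split 3:1 is 6 + 2, as protocol 9.5 states. A full four-period cohort has 4 × 2 = 8 placebo slots for 8 people, a mean of one each.

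**Inputs.**
- M, the pooled placebo participant-periods. If each of the six doses in protocol Table 3 takes one SDD escalation period, M = 6 × 2 = 12. If all eight periods of Cohorts 1 and 2 were escalation periods, M = 16.
- K, the participants with two pooled placebo periods. It depends on a randomization schedule that is not shown. At M = 12 it can be 0 to 6.
- p, the chance of meeting a criterion in one period, and ρ, the within-person correlation. Neither is in the documents; both are assumed.

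**Formula.** For a person with two periods, P(at least one qualifies) = p(2 − p) − ρp(1 − p) = p[1 + (1 − p)(1 − ρ)]. There are M − K distinct participants, of whom M − 2K have one period. The expected placebo proportion counted by participant is therefore

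[(M − 2K)p + K·p{1 + (1 − p)(1 − ρ)}] / (M − K) = p{1 + [K/(M − K)](1 − p)(1 − ρ)}.

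Counted by participant-period it is p. The two agree if K = 0 or ρ = 1.

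**Results.**

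| M | K | p | ρ = 0 | ρ = 0.5 |
|---|---|---|---|---|
| 12 | 2 | 2% | 2.4% | 2.2% |
| 12 | 2 | 10% | 11.8% | 10.9% |
| 12 | 3 | 10% | 13.0% | 11.5% |
| 16 | 4 | 10% | 13.0% | 11.5% |
| 12 | 6 (extreme) | 10% | 19.0% | 14.5% |

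For example, M = 12, K = 2, p = 10%, ρ = 0: 0.10 × (1 + 0.2 × 0.9) = 0.118. A true contrast of 30% against 10%, which is 20 points, would then show as 30 − 11.8 = 18.2 points, or 30 − 10.9 = 19.1 at ρ = 0.5. One participant in a six-person dose column is 1/6 = 16.7 points.

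**The shift is an average, not a rule.** Take M = 12, K = 2, and suppose the only qualifier is a double-placebo participant who qualifies in both periods. By period the figure is 2/12 = 16.7%; by participant it is 1/10 = 10%. Exact enumeration at p = 10% and ρ = 0.5 puts the participant percentage below the period percentage in 10.6% of tables, equal in 31.5% and above in 57.8%.

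**The wording side by side.** The three sections that define these tables agree on participants. SAP 5.2.2 is a general line, and SAP 5.2.1 uses the same phrase, number of observations, as its label for the count of continuous data. Baseline is reset each period, so change from baseline has to be derived within period. That fixes how a maximum is found; it does not fix a table's denominator. Counting a person once if any placebo period qualifies fits all of these passages.

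**The case for a change.** The strongest case for a change is that preferring the specific text over the general does not supply the missing rule. SAP 5.2.2, unlike 5.2.1, carries no exception clause. The PR categories in SAP Appendix 1 depend on baseline, which is per period, so one person could fall into different PR categories in two placebo periods. Two placebo periods are also likely to occur. In a fully dosed four-period cohort, anyone who receives four active doses has no placebo, so someone else must have two. If placebo were drawn independently in each period with a cap of two (an assumption), about 2.2 of 8 participants per cohort would have two. A sentence or a footnote would be cheap.

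Most of this stands as description. The convention is not written in what was supplied, and the expected shift is upward when K is above zero and ρ is below 1. It does not follow that the plan must change. The actual schedule may give everyone one placebo period, and both periods must be SDD escalation periods to be pooled at all. The sponsor standards may already set the unit. Counting participants with at least one qualifying value is a legitimate summary that the protocol itself names; counting periods instead would let one person enter the column twice. The choice is a trade-off, not a correction.

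**Conclusion.** The concern does not call for a change. What is left is an unstated convention for a participant with two pooled placebo periods, which analysts can settle in the table shells or from the sponsor standard. A footnote giving distinct participants and participant-periods for pooled placebo would be a courtesy to readers, and the unit in protocol 9.3.1.1 can stay as it is.

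If such participants exist and each is counted once, the expected placebo percentage at p = 10% rises by 0.9 to 1.8 points with M = 12 and K = 2, and by 1.5 to 3.0 points with K = 3 or with M = 16 and K = 4. At p = 2% with M = 12 and K = 2 it rises by 0.2 to 0.4 points. Only the extreme allocation of K = 6 gives more, 4.5 to 9.0 points at p = 10%. These figures rest on assumed p, on ρ between 0 and 0.5, and on an unseen schedule.

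No conclusion turns on this. SAP 5.1 excludes hypothesis tests and statistical decision rules. The stopping criteria in protocol 6.6.1 count events in participants on active drug and use no pooled placebo percentage. SAP 6.1.3 and Appendix 1 require qualifying values to be listed, so a reader can recount on either basis.
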